6.1.1 Dosage Form and Mode of Administration

The tablets are scored in a way that they can be split into two halves that maintain the release characteristics of the whole tablets. Depending on the cohort, study participants will take either 1 half-tablet (300 mg), 1 tablet (600 mg), 1.5 tablets (900 mg), or 2 tablets (1200 mg) twice a day, at least 8 hours apart. Patients in Cohorts 1 and 3 will be instructed to cut their tablets on an as-needed basis, not all at once upon receipt of the medication. The route of administration is oral.

6.1.2 Precautions for Use

The tablets are to be stored at 15–30°C in a tightly closed bottle in order to protect them from moisture and light, and the bottle kept out of the reach and sight of children.

The study product can be taken with or without food.

6.2 Reference Product

Placebo tablets are identical in appearance to the deferiprone delayed release tablets. Within each cohort, the number of placebo tablets taken at each dose will match that of the corresponding active product: i.e., 1 half-tablet, 1 tablet, 1.5 tablets, or 2 tablets. Placebo tablets will be taken twice a day, at least 8 hours apart.

6.3 Packaging and Labeling

The study products will be supplied in high-density polyethylene (HDPE) bottles with child-resistant closure, containing 100 tablets each. Each bottle will contain a desiccant bag.

The bottles will be provided with a label whose content is in accordance with all applicable regulatory requirements. The label will include protocol number, expiry date, lot/batch number,

investigational statement, storage temperature, dosage, direction for use, visit number, date dispensed, and name and address of the sponsor.

6.4 Shipping and Storage

The study medication at each site will be kept in a secure location (a locked room or cabinet) under adequate storage conditions, as per label requirements, under the control of the investigator and with access to authorized individuals only. Product is to be kept at room temperature (15–30 °C / 59–86 °F). The room must have a calibrated digital temperaturemonitoring device, and site personnel must use a temperature log to facilitate daily recording of the temperature of the storage facility. Temperature deviations must be immediately reported to the sponsor for investigation and determination of impact on the study medication.

Each shipment of investigational product will include shipment documents, which the investigator or a designate must complete as per the provided instructions and retain the original copies in the Investigator Trial File.

6.5 Dispensing Procedures

Patients will be dispensed a 2-month supply of study medication at baseline, Month 2, and Month 4, and a 3-month supply at Month 6. Dispensing of study medication must be done by appropriately qualified staff (e.g., physician, pharmacist, or nurse).

Patients will be dispensed a sufficient amount of study medication, with an allowance for the visit windows of ± 5 days. Each bottle of deferiprone-DR or placebo contains 100 tablets. Hence, the following quantities will be provided:

	Baseline, Month 2, and Month 4	Month 6
Cohort 1	1 bottle	2 bottles
Cohort 2	2 bottles	3 bottles
Cohort 3	3 bottles	4 bottles
Cohort 4	3 bottles	5 bottles

6.6 Product Accountability

The investigator must maintain an updated Site Investigational Drug Inventory Record at the study site. This log will include at a minimum:

• Name of sponsor

- Name of investigator
- Study identifier
- Date and quantity of investigational product received from sponsor
- Lot/batch number

For each patient, the investigator must maintain an updated Patient Investigational Drug Dispensing Record. This log will include at a minimum:

- Patient identification number
- Date of dispensing and return
- Dispenser's initials
- Quantity dispensed and returned

At the conclusion of the study, a final inventory must be performed by the investigator (or delegate). If any tablets or bottles are missing, this must be indicated on the study drug accountability form, together with an explanation of the discrepancy. These forms must be available for sponsor clinical monitoring as well as for sponsor audit and regulatory authority inspection purposes at any time.

It is the responsibility of the investigator to ensure that all study drug received at the site is inventoried and accounted for throughout the study. Records of receipt, storage, and administration of the study drug supplied must be maintained, and the drug accountability will be verified by the sponsor or sponsor's designee during on-site monitoring visits. The sponsor will be responsible for determining the specific conditions for destruction of unused product.

6.7 Replacement Doses

Patients who report that their medication has been lost or damaged will need to return to the study site to receive replacement tablets. Requests for replacement must be made in writing to the sponsor by the qualified staff member, and the study coordinator must contact the IVRS/IWRS again to ensure that the patient is provided with the correct product. All information related to the lost or damaged medication and the replacement medication is to be recorded in the drug accountability forms and patient source data.

6.8 Disposition of Unused Product

All investigational product that has been returned by the patient or that is unused for any other reasons will be returned to the sponsor or discarded by the site according to internal procedures, if approved, in writing, by the sponsor. The destruction procedures must include the issuance of appropriate signed destruction certificates including mode of destruction and

complete drug accountability of destroyed materials. The destruction may take place only after written approval by the sponsor.

6.9 Other Study Supplies

All required study supplies, including but not limited to diary cards and laboratory kits, will be provided by the sponsor to the sites.

7 MEASUREMENTS AND EVALUATIONS

7.1 Efficacy Measurements

Efficacy will be measured using 1) the Movement Disorder Society-Unified Parkinson's Disease Rating Scale (MDS-UPDRS), 2) the Montreal Cognitive Assessment (MoCA) test, 3) pharmacodynamic biomarkers, and 4) mechanism of action biomarkers.

7.1.1 Primary Efficacy Measurements

7.1.1.1 Motor Score on the Unified Parkinson's Disease Rating Scale

The MDS-UPDRS is the most recent version of the major rating scale used to assess the severity of symptoms of PD. It consists of 4 parts: Part I, non-motor experiences of daily living; Part II, motor experiences of daily living; Part III, motor examination; and Part IV, motor complications. Part I has two components: I-A concerns a number of behaviors that are assessed by the investigator using all pertinent information from patient and caregiver, and I-B is completed by the patient with or without the aid of the caregiver, but independently of the investigator. These sections can, however, be reviewed by the rater to ensure that all questions are answered clearly, and the rater can help explain any perceived ambiguities. Part II is designed to be a self-administered questionnaire, but can be reviewed by the investigator to ensure completeness and clarity. Part III has instructions for the rater to give or demonstrate to the patient; it is completed by the rater. Part IV has instructions for the rater and also instructions to be read to the patient. This part integrates patient-derived information with the rater's clinical observations and judgments, and is completed by the rater. Each time the MDS-UPDRS is completed, both individual subscale scores and a total score are generated. The MDS-UPDRS is to always be administered by the same qualified investigator, at approximately the same time (early in the morning).

The primary measurement for efficacy in this study is the score on the motor examination section (Part III). It will be obtained at baseline and Months 3, 6, and 9.

7.1.2 Secondary Efficacy Measurements

7.1.2.1 Total Score on the Unified Parkinson's Disease Rating Scale

The total score derived from all of the MDS-UPDRS subscale scores will be obtained at baseline and Months 3, 6, and 9.

7.1.2.2 Other Scores on the Unified Parkinson's Disease Rating Scale

The individual scores derived from the MDS-UPDRS Part I (non-motor experiences of daily living), Part II (motor experiences of daily living), and Part IV (motor complications) as well as the combined score from Parts II and III will be obtained at baseline and Months 3, 6, and 9.

7.1.2.3 Montreal Cognitive Assessment Test

The Montreal Cognitive Assessment (MoCA) test is a rapid screening instrument (administration time around 10 minutes) for the detection of mild cognitive dysfunction. It is used to assess the following cognitive domains: short-term memory recall, visuospatial abilities, executive functions, attention, concentration, working memory, language, and orientation to time and place. The full version of the scale will be used in this study.

The MoCA will be completed at baseline and Months 3, 6, and 9. It is always to be administered by the same qualified investigator, at approximately the same time (early in the morning).

7.1.2.4 Oxidative Stress Biomarkers

Free radicals, oxygen-containing molecules with one or more unpaired electrons, are highly reactive with other molecules and will appropriate their electrons in order to become stabilized; this triggers a chain of reactions as each target molecule in turn seeks to appropriate an electron from another, and can result in serious damage to cell components including lipids, proteins, and DNA. Antioxidants are molecules within cells that prevent these chain reactions by donating an electron to the free radicals without becoming destabilized themselves. When there is an imbalance between oxidants and antioxidants, i.e., when the production of free radicals surpasses a cell's ability to counteract or detoxify their harmful effects through neutralization by antioxidants, the result is oxidative stress. This condition is seen in various neurodegenerative disorders, including Parkinson's disease. Hence, measuring biomarkers that are indicators of oxidative stress may serve as a measure of progression or improvement of disease.

The oxidative stress biomarkers of total antioxidant status, protein carbonyls, glutathione, and super-oxide dismutase will be measured in a panel of blood/serum tests at baseline and Months 3, 6, and 9. The oxidative stress biomarkers of 8-OHdG and of malondialdehyde, which results from lipid peroxidation of polyunsaturated fatty acids, will be assessed in urine at these same time points.

7.1.2.5 Inflammatory Factor Biomarkers

Numerous studies have indicated the presence of an inflammatory process in PD. Hence, biomarkers of such processes may serve as a measure of worsening or improvement of disease.

The inflammatory factor biomarkers of TNF alpha and IL-6 will be measured in a panel of blood tests at baseline and Months 3, 6, and 9.

7.1.3 Exploratory Efficacy Measurements

Mechanism of Action (MOA) biomarkers will be examined to evaluate whether specific genotypes of enzymes that play a role in Parkinson's disease affect the potential disease-modifying action of deferiprone.

7.1.3.1 D544E (AT) Polymorphisms of Ceruloplasmin

Ceruloplasmin is a glycoprotein that plays a role in the oxidation of iron, oxidizing toxic ferrous iron (Fe2+) into ferric iron (Fe3+) and enabling iron transportation between blood and cells. The genotypes AT and AA determine whether an individual is a low or a high metabolizer of ceruloplasmin, respectively. Individuals with the AT genotype, who are low metabolizers, have lower ceruloplasmin ferroxidase activity, which may result in increased brain iron overload.

A blood sample for the determination of ceruloplasmin genotype will be taken at baseline.

7.1.3.2 Ceruloplasmin Levels and Ceruloplasmin Ferroxidase Activity

Blood samples for the measurement of ceruloplasmin levels and ceruloplasmin ferroxidase activity will be collected at baseline and Months 3, 6, and 9.

7.1.3.3 V158M Polymorphisms of Catechol O-methyltransferase

Catechol O-methyltransferase (COMT) is a metabolic enzyme that participates in the inactivation of dopamine and other neurotransmitters. The Val158Met (V158M) polymorphism of COMT is associated with Parkinson's disease.

A blood sample for the determination of the COMT genotype will be taken at baseline.

7.2 Safety Measurements

7.2.1 Medical Events, Adverse Events, and Serious Adverse Events

7.2.1.1 Definition of Medical Events and Adverse Events

Medical Event (ME): Any new untoward medical occurrence or worsening of a pre-existing condition in a clinical trial participant that occurs after signing the informed consent form (ICF) but before receiving the first dose of study drug.

Adverse Event (AE): Any untoward medical occurrence in a patient who is administered a pharmaceutical or other therapeutic product in a clinical study, not necessarily having a causal relationship with the product. An AE can therefore be any unfavorable and unintended sign, symptom, or disease temporally associated with the use of a product, whether or not considered related to that product.

AEs include:

- Exacerbation of a pre-existing illness, including acute episodes/crisis of a chronic underlying condition
- An increase in frequency or intensity of a pre-existing episodic event or condition
- A condition detected or diagnosed after study treatment administration, even though it may have been present prior to the start of the study
- A continuous persistent disease or symptom present at baseline that worsens following the start of the study
- Accidents (e.g., involving a motor vehicle)
- Reasons for changes in concomitant medication (type of drug and/or dose)
- Medical, nursing, or pharmacy consultation
- Admission to hospital and surgical operations
- Abnormalities in laboratory findings (e.g., clinical chemistry, hematology, urinalysis),
 ECG, or other assessments (e.g., vital signs) that are not part of a larger medical
 condition already recorded as an AE and which are judged by the investigator to be
 clinically significant. The investigator should exercise medical and scientific judgment in
 deciding whether an abnormal laboratory finding or other abnormal assessment is
 clinically significant.

AEs do not include:

- A pre-existing disease or condition present or detected at the start of the study that does not worsen
- Hospital admissions or surgical procedures that had been planned prior to enrolment into the study
- The disease or disorder being studied, or a sign or symptom associated with that disease or disorder, unless it has worsened
- An overdose of either the study treatment or concurrent medication without any signs or symptoms

7.2.1.2 Monitoring and Documenting of Medical Events and Adverse Events

Prior to enrolling a patient, study site personnel will note the occurrence and nature of any medical condition(s) in the source documents and the appropriate section of the eCRF. During the study, they will note any change in the condition(s), and the occurrence and nature of any MEs/AEs. MEs will be collected from the time the ICF is signed until the first dose of study drug; non-serious AEs will be collected from the first dose until the final day of dosing; AEs that are still ongoing at the time of study termination will be followed until resolution or stabilization of the event or its sequelae; and serious AEs will be collected from the first dose until 30 days after the last dose of study medication.

AEs and SAEs that are related to the underlying medical condition for which the patient enrolled in the clinical trial will be recorded separately from others.

Patients will be instructed to report any MEs/AEs to the investigator or a delegate. In addition, the investigator will solicit information about the occurrence of MEs/AEs through open-ended, non-leading verbal questions such as:

- How are you feeling?
- Have you had any medical problems since the last visit?
- Have you taken any new medications, other than those provided in this study, since the last visit?

Based on the patient's response to these questions, the investigator or delegate should ask additional questions relevant to the specific complaint, such as:

- How severe is/was the symptom?
- How often did the symptom occur?
- How long did the symptom last?

The patient should also be questioned about any previously reported AEs that have not resolved.

The investigator will evaluate all AEs/MEs for their relationship to the investigational product (Section 7.2.1.3), intensity (Section 7.2.1.4), and seriousness (Section 7.2.1.5), and will document any measures taken to address the event. There should be an attempt to establish a diagnosis of the AE based on signs, symptoms, and/or other clinical information. Wherever possible, a diagnosis should be documented, rather than the individual signs/ symptoms. All information is to be clearly recorded in the source documents.

If the dosage of study drug is reduced or treatment is discontinued as a result of an AE, the circumstances leading to such reduction or discontinuation must be clearly documented.

All AEs must be followed until resolution, the condition stabilizes, the event is otherwise explained, or the patient is lost to follow-up. The investigator is responsible for ensuring that follow-up includes any supplemental investigations that are needed to elucidate the nature and/or causality of the AE as completely as possible. This may include additional laboratory tests or investigations, histopathological examinations, or consultation with other health care professionals.

7.2.1.3 Assessment of Causality

The relationship of an AE to the study drug should be determined by the investigator after thorough consideration of all available facts, including associative connections (time or place), pharmacological explanations, previous knowledge of the drug, presence of characteristic clinical or pathological phenomena, exclusion of other causes, and/or absence of alternative explanations. The causal relationship of an adverse event to study drug will be assessed according to the following criteria (based on World Health Organization definitions):

• Not related: Temporal relationship to study drug administration is missing or

implausible, or there is no evident cause.

• Possibly related: Reasonable time sequence to administration of study drug, but

event could also be explained by concurrent disease or other drugs

or chemicals.

• Probably related: Reasonable time sequence to administration of study drug, and

unlikely to be attributed to concurrent disease or other drugs or chemicals, and follows a clinically reasonable response on

withdrawal (de-challenge). Re-challenge information is not required.

Definitely related: Plausible time relationship to study drug administration, and cannot

be explained by concurrent disease or other drugs or chemicals. The

response to withdrawal of the drug (de-challenge) should be

clinically plausible. The event must be definitive pharmacologically or phenomenologically, using a satisfactory re-challenge procedure

if necessary.

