7.2.1.6 Reporting of Serious Adverse Events

All SAEs occurring up to 30 days following the last dose of study medication must be reported to the sponsor, regardless of whether they are suspected of having a causal relationship with the study drug. Any SAEs for which the investigator does suspect a causal relationship must be reported to the sponsor regardless of the time elapsed since the last dose of the study drug.

Patients will be instructed to report SAEs to the investigator within 24 hours, by telephone. In turn, the investigator must report all SAEs to the sponsor within 24 hours of occurrence or notification by the patient, using the sponsor's SAE form. The sponsor will provide contact information for reporting SAEs. An assessment of causality must be provided at the time of the initial report. The investigator or delegate must then complete and submit a follow-up SAE form to the sponsor within 5 calendar days, and must submit further follow-up forms if additional relevant follow-up information becomes available.

The sponsor will submit reports of SAEs to the appropriate regulatory agencies, in line with local regulatory requirements and timelines.

Investigators must report all SAEs to their IRB/IEC, as per local policy, as well as to the sponsor. If any SAE that is considered at least possibly related to the study medication and is unexpected occurs at one site, the sponsor will promptly inform all other sites of this, and all investigators must then report this event to their own IRBs/IECs, following the same timelines as above or following local IRB/IEC policy, whichever takes precedence.

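### The causality scale can be read to rate a well-timed, unexplained adverse event as not related, and it offers that event no related category

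*Protocol*

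**What the plan says.** Protocol 7.2.1.3 opens by asking the investigator to weigh all available facts, among them "exclusion of other causes, and/or absence of alternative explanations". It then makes four categories the criteria by which causality is assessed:

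- *Not related*: the time link to dosing is missing or "implausible, or there is no evident cause".
- *Possibly related*: the time sequence is reasonable, but the "event could also be explained by concurrent disease or other drugs" or chemicals.
- *Probably related*: the time sequence is reasonable, other causes are unlikely, and there is a sensible response once the drug is withdrawn.
- *Definitely related*: the timing is plausible, other explanations are ruled out, the withdrawal response should be plausible, and the event must be definitive on pharmacological or phenomenological grounds.

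Protocol 7.2.1.2 has the investigator apply these criteria to every AE. Relatedness is a named safety endpoint in 9.1.4. Section 9.4.1.4 counts patients with a drug-related AE, splits AEs into those at least possibly related and those not related, and counts a patient with several events by the one most closely related. The same threshold governs the DSMB evaluation in Section 8 and the notice to other sites in 7.2.1.6.

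**The concern.** The two grounds for *Not related* are joined by an *or*, so the second applies whatever the timing. Lack of any evident cause then counts against the drug's involvement, although the lead-in lists absence of alternative explanations among the facts to weigh. A well-timed event with a rival explanation reaches *Possibly related*. The same event with the rival explanation removed can fall to *Not related*.

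This study is meant to find the dose with the best balance of benefit and risk (Protocol 3.3), and the relatedness split is part of its safety description. Sites apply the scale when they record each event. A later analysis can tabulate the ratings but cannot repair them. For non-serious AEs, the investigator's rating is the only one the protocol describes.

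**Working it through.** The protocol gives no figure to reproduce, so the check is to run one event through the four definitions.

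**Test event.** The timing is reasonable, no alternative explanation has been identified that the investigator could put forward, and de-challenge information is absent or inconclusive.

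| Reading of the clause | *Not related* | *Possibly* | *Probably* | *Definitely* |
|---|---|---|---|---|
| No evident cause of any kind (literal) | met | not met: no rival explanation | not met: no withdrawal response | not met |
| No evident link to the drug, and timing alone is not such a link | met | not met | not met | not met |
| No evident link to the drug, but timing is taken as one; or the drug itself is the evident cause | not met | not met | not met | not met |

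Under the first two readings the event is *Not related*. Under the third it has no category. Under none does it meet the text of a related category.

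One assumption lies in the last column. *Definitely* says the withdrawal response should be plausible, which is softer than a requirement. Even so, it also demands a definitive event, and one whose cause is unexplained would hardly qualify.

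**Comparison event.** Add a concurrent disease or another drug that could account for the event. *Possibly related* is now met, so the event with the weaker case against the drug is the one counted as related.

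**Overlap.** If the unexplained event instead resolves on withdrawal, the literal clause and *Probably related* are both met. The clause therefore also stops the categories from being exclusive.

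**Can de-challenge information be missing?** Yes. Protocol 7.2.1.2 treats a change of dosing as conditional: "If the dosage of study drug is reduced or treatment is discontinued as a result of an AE". Dosing may continue through many AEs. For SAEs, 7.2.1.6 asks for a causality assessment with the initial report, due within 24 hours, when the response to withdrawal may not yet be known. Follow-up forms can update it.

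**Where the rating goes.**

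- *9.4.1.4:* the event leaves the related side of the split. The patient leaves the drug-related count unless another of that patient's AEs is rated at least possibly related.
- *7.2.1.6:* the cross-site notice begins "If any SAE that is considered at least possibly related to the study medication and is unexpected occurs at one site". It does not confine that judgement to the investigator.
- *Section 8:* a death or life-threatening event reaches the DSMB if either the investigator or the sponsor thinks it at least possibly related.
- *Unaffected:* AE tables by treatment group that do not use relatedness.

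**The case against.** The strongest reply is that *could also be explained* is a low bar. Every patient has Parkinson's disease and takes antiparkinsonian medication, so many well-timed events can be rated *Possibly related* without strain. This stands, and it narrows the point to events for which the investigator can offer no such explanation. A reader might infer that a sudden unexplained death must be rated *Not related* and so escape the DSMB. The text does not support that: undiagnosed concurrent disease could explain such a death, and the sponsor can trigger the evaluation itself.

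Second, the lead-in asks for judgement on all the facts, and the clause may have been meant as no evident link to the drug. That is a fair reading, but it does not rescue the scale, because the event still meets no related category. An investigator who chooses *Possibly related* must depart from the criterion as written.

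Third, a reader might infer that the drug's main known risk would be under-attributed. The protocol does not bear this out. Treatment interruption is mandatory for confirmed mild or moderate neutropenia and for any single ANC below 0.5 × 10⁹/L (7.2.1.8.1), and for fever or infection (4.5.3, 7.2.1.8.2). De-challenge information will usually exist there.

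Fourth, there are safeguards. Protocol 7.2.1.6 provides that "All SAEs occurring up to 30 days following the last dose of study medication must be reported to the sponsor", whatever the suspected cause, and 7.2.1.2 requires follow-up to include "any supplemental investigations that are needed to elucidate the nature and/or causality of the AE as completely as possible". These protect the SAE pathway. They do not repair the descriptive split for non-serious AEs, for which no sponsor re-rating is described.

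Finally, one might try to size the problem by listing combinations of criteria. The text grades other explanations in three steps (could, unlikely, cannot), which a yes/no listing cannot represent, and combinations are not frequencies. No such count is offered.

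**Conclusion.** The point holds in limited form. The clause can be read to rate a well-timed AE with no identified alternative explanation and no de-challenge information as *Not related*, contrary to the section's own lead-in. On the gentler readings the event still satisfies none of the related definitions.

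The firm consequence is descriptive: the related/not-related split and the drug-related AE count. The DSMB trigger and the cross-site notice are affected only if the sponsor does not itself judge the event related. The size cannot be derived, because the protocol gives no rate for such events. A reader might infer that AE comparisons between arms are distorted in general. They are not, since the overall tables by treatment group do not use relatedness, and no efficacy conclusion depends on it.

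The conclusion rests on taking the four definitions as the operative rule and on treating the withdrawal response as needed for *Probably* and, in practice, for *Definitely*. The fault is worth correcting because the rule misclassifies as written and the repair is small.

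**What to change.** In Protocol 7.2.1.3:

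1. Delete the second ground from *Not related*, or replace it with: *or there is no reasonable possibility of a relationship to the study drug*.
2. Add that an event with a reasonable time sequence, no identified alternative explanation, and absent or inconclusive de-challenge information is rated at least *Possibly related*.
3. Leave unexplained events with a negative de-challenge to the investigator's judgement. Neither forcing these into *Possibly related* nor requiring positive proof of another cause before *Not related* can be used is needed to cure the defect.
4. Align the eCRF and the SAE form if they repeat the present wording; neither is shown.

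The cost is a wording amendment. The downside is that somewhat more events in all arms, placebo included, will be counted as possibly related, and a few more may reach the DSMB or prompt a notice to other sites.
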